8.5. Vital Signs

Vital signs (systolic blood pressure, diastolic blood pressure, heart rate, arterial oxygen saturation level (%), weight and BMI) are assessed at all study visits as described in [Appendix 1: Time and Event Schedule](#). For vital signs parameters, absolute values and change from baseline will be presented by means of descriptive statistics at all scheduled study visits.

All data will be included in data listings.

8.6. Electrocardiogram (ECG)

A 12-lead electrocardiogram (ECG) (PR, RR, QRS, uncorrected QT, corrected QTcB, corrected QTcF) is assessed at the study visits described in [Appendix 1: Time and Event Schedule](#). At each scheduled visit Investigator will provide overall ECG evaluation classifying the ECG as normal, abnormal NCS and abnormal CS.

Overall ECG evaluation by visit and shifts from baseline over all post-baseline results will be presented for overall ECG evaluation displaying normal, abnormal NCS and abnormal CS values.

All data will be included in data listings.

8.7. Echocardiogram

Echocardiogram is assessed at the study visits described in [Appendix 1: Time and Event Schedule](#).

Following parameters will be evaluated:

- Left Ventricular Ejection Fraction (%) (LVEF)
- Left ventricular mass
- Left ventricular volume
- Left Ventricular End Diastolic Dimension (LVEDD)
- Left atrial size
- Left atrial volume
- Mitral regurgitation
- Systolic pulmonary artery pressure (sPAP)
- Diastolic pulmonary artery pressure (dPAP)
- Mean pulmonary artery pressure (mPAP)
- Tricuspid regurgitation Peak Velocity
- End Diastolic Pulmonary Regurgitation Gradients

This document is confidential.

- Right atrial pressure (RAP)
- Overall Interpretation

At each visit Investigator will provide Overall interpretation evaluation classifying the Echocardiogram as normal, abnormal NCS and abnormal CS.

Overall interpretation by visit and shifts from screening to Visit 6 (Month 12) will be presented for overall interpretation displaying normal, abnormal NCS and abnormal CS values.

All data will be included in data listings.

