4 POTENTIAL RISKS AND BENEFITS

4.1 Potential Risks

There is extensive clinical experience with respect to right heart cardiac catheterization and interventional procedures, and it is expected that these acute procedural risks will not be significantly different with the Cordella PA Sensor System. Possible adverse events associated with cardiac catheterization and/or the implantation of the Cordella PA Sensor System may include, but are not limited to, the following:

- Allergic reaction
- Arrhythmias
- Bleeding complications (which may require transfusion)
- Cardiac arrest
- Chest pain
- Death
- Device embolization/migration
- Device explant
- Emergent or urgent cardiac, vascular, and/ or other surgery necessitated by the device or implant procedure (e.g., coronary sinus lead revision)
- Endocarditis or device infection
- Entry site complications (e.g., hematoma, dissection)
- Fracture of a component of the device/system that may or may not lead to serious injury or surgical intervention
- Gastrointestinal bleed (antiplatelet therapy)
- Hemoptysis
- Hypo or hypertension
- Infection or fever
- Peripheral embolism/thrombus
- Pulmonary embolism/pulmonary occlusion
- Pseudoaneurysm of the vein
- Radiation exposure
- Reaction to contrast media/ medication
- Renal insufficiency or failure
- Respiratory distress or failure (breathing problems)
- Sepsis
- Valvular injury (tricuspid and/or pulmonary)
- Vascular complications (e.g., venous dissection, perforation, rupture, arteriovenous fistula)
- Vessel trauma which may require surgical repair

- Worsening heart failure

When used in accordance with the clinical protocol, risks associated with commercially available Cordella System are considered low. To ensure proper use of the myCordella™ Tablet and Peripherals, subjects will be trained in accordance with the manufacturer's instructions for use. Potential risks of the commercially available Cordella System include the following:

- Temporary arm discomfort/pressure from the blood pressure cuff
- Skin irritation or petechia at the site of the blood pressure cuff placement
- Loss of balance while standing on scale
- Inaccurate measurements or measurement errors

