8.1.10 Echocardiogram

Echocardiograms will be performed at Screening, Month 12 and Year 3, 4 and 5.

Echocardiograms will determine the following parameters:

- LVEF
- Left ventricular mass
- Left ventricular volume
- Left Ventricular End Diastolic Diameter (LVEDD)
- Systolic pulmonary artery pressure (sPAP)
- Mean pulmonary artery pressure (mPAP)
- Diastolic pulmonary artery pressure (dPAP)
- Right atrial pressure (RAP)
- Left atrial size
- Left atrial volume
- Mitral regurgitation
- Tricuspid regurgitation

If an echocardiogram has been performed within 3 months of Screening, that LVEF may be acceptable to determine study eligibility. While an echocardiogram within 3 months of the screening visit date is preferable. In case this is not possible, Endotronix will accept an echocardiogram from within 6 months of Screening provided the patient does not have a standard of care indication for an echocardiogram during this interval.

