9.3 Adverse Event Reporting Requirements

9.3.1 Investigator Reporting Requirements

All AEs, regardless of seriousness, severity, or presumed relationship to study therapy, must be recorded using medical terminology in the source document and in the eCRF. Whenever possible, diagnoses should be given when signs and symptoms are due to a common etiology (e.g., cough, runny nose, sneezing, sore throat, and head congestion should be reported as "upper respiratory infection"). Investigators must record in the eCRF their opinion concerning the relationship of the AE to study therapy. All measures required for AE management must be recorded in the source document and reported according to Endotronix instructions.

All events will be classified per Adverse Event definitions as documented in Appendix 14.7. Additionally, the date of the event, seriousness criteria and outcome should also be recorded.

Laboratory and clinical parameters will be followed to evaluate the safety and performance of the Cordella PA Sensor System; these include adverse event reporting and monitoring, routine clinical laboratory tests (hematology, biochemistry, and urinalysis), vital signs, review of concomitant medications and echocardiogram.

It is the responsibility of the investigators to inform their IRB/IEC of adverse events as required by their local IRB procedures.

Investigators must notify Endotronix (or designee) within 24 hours of discovering any Unanticipated Adverse Device Effects (UADE)/ Unanticipated Serious Adverse Device Effect (USADE). Investigators are required to submit a report of a UADE/ USADE to the reviewing IRB/ IEC as soon as possible, but in no event later than 10 working days after the investigator first learns of the event. UADEs/USADEs must be documented on the appropriate eCRF.

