7.1.17. Functional status improvement measured by NYHA and 6-Minute Walk Test

NYHA functional classification: The subject's functional status is assessed by a qualified individual at the institution, who is not directly involved with this clinical trial, by utilizing the NYHA functional classification, described in the Protocol Appendix 14.2.

The NYHA functional classification categorizes the extent of heart failure by placing subjects in one of four (I, II, III, IV) categories based on how much they are limited during physical activity and symptoms of shortness of breath and/or angina.

This document is confidential.

NYHA functional classification will be obtained at all study visits as described in [Appendix 1: Time and Event Schedule](#) and must be NYHA Class III for study entry.

Shifts in NYHA functional classification from baseline over all post-baseline visits will be presented.

Six (6) Minute Walk: Subjects complete a six (6) minute walk test at the study visits described in [Appendix 1: Time and Event Schedule](#). Total distance walked (meters) will be collected and analyzed by means of descriptive statistics including the absolute value and change from baseline by visit.

Analysis will be done based on mITT population, PP population, and Cohort #1 population. Prior to the date of cut-off for the main analysis, it will be confirmed, if analysis based on PP population will be required.

This document is confidential.

8. Safety

The population used for safety analyses will be the ITT. Safety will be assessed on the basis of adverse events (AEs), clinical laboratory data, ECG parameters, Echocardiograms, physical examinations, and vital signs. Primary safety endpoint will be analyzed based on mITT. In addition, AEs will be analyzed based on Cohort #1 population. Primary safety endpoints will also be repeated on ITT, PP population and Cohort #1 population. Secondary safety endpoints will also be analyzed based on PP population and Cohort #1 population. For CEC related endpoints, tables and figures will be repeated using CEC adjudication results

Adverse events and other safety analyses will also be assessed. No formal statistical hypothesis tests will be conducted. Analyses will involve Kaplan-Meier curves for time to event outcomes, descriptive statistics (n, mean, standard deviation, median, minimum, and maximum) for quantitative outcomes, and count and frequency results for categorical outcomes.

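### SAP 8.7 summarises echocardiograms only by a three-level overall interpretation, so change at the tricuspid or pulmonary valve, a named risk, is listed per subject but never tabulated against Screening

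*SAP*

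**What the plan says.** **Risk.** Protocol 4.1 lists among possible complications "Valvular injury (tricuspid and/or pulmonary"). The same item stands in the anticipated-event table of Protocol 9.1.4, with its incidence marked as not available.

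**Measurement.** Protocol 9.3.1 says "Laboratory and clinical parameters will be followed to evaluate the safety and performance of the Cordella PA Sensor System" and counts the echocardiogram among those parameters. Protocol 8.1.10 sets the schedule: "Echocardiograms will be performed at Screening, Month 12 and Year 3, 4 and 5". Its parameter list includes "Tricuspid regurgitation" and no pulmonary valve measure.

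**Analysis.** SAP 8.7 lists 13 parameters plus the overall interpretation. The tricuspid item there reads "Tricuspid regurgitation Peak Velocity", and a pulmonary item has been added, "End Diastolic Pulmonary Regurgitation Gradients". Two summaries are planned. One tabulates the investigator's overall reading at each visit. The SAP describes the other in these words: "shifts from screening to Visit 6 (Month 12) will be presented for overall interpretation displaying normal, abnormal NCS and abnormal CS values". All values go into subject listings (16.2.8.2.3, and 16.2.8.2.3.1 for Cohort #1). The index holds four echocardiogram tables, 14.3.4.4.1 to 14.3.4.4.4, two on ITT and two on Cohort #1, all on the overall evaluation. The opening text of SAP section 8, like Protocol 10.7, says that safety analyses will involve "descriptive statistics (n, mean, standard deviation, median, minimum, and maximum) for quantitative outcomes".

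**The concern.** The sensor is delivered through a vein into the pulmonary artery (Protocol 2.1), so the catheter passes both right-heart valves. The protocol treats valve injury as a recognised risk whose frequency is unknown, and it schedules the examination that could describe it. The SAP then condenses that examination into one label covering the whole heart.

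At stake is a descriptive safety result. The trial could report how often tricuspid or pulmonary regurgitation worsened after implant. As planned, any change that is not reported as an adverse event stays in the listings, and nobody is asked to count it.

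**Working it through.** The plan states no echocardiographic event rate, sample size or power, so there is no figure to reproduce. The check has four parts.

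**1. Where a new valve lesion would surface**

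| Situation | Where it appears |
|---|---|
| Reported as an adverse event | Tables by system organ class and preferred term; anticipated-event tables 14.3.1.25 to 14.3.1.27; implant-procedure tables if judged related |
| Device or system related, and treated invasively, fatal or leading to explant | Primary safety endpoint (definition in Protocol 9.4) |
| Not reported, but the investigator moves the overall reading to a worse level | Shift table, with no indication of the valve |
| Not reported, and the overall reading does not change | Subject listing only |

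Valve injury is not one of the predefined event categories in SAP 8.3.3. It would fall under the final category for other events.

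**2. Comparison with other safety data in the SAP**

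Vital signs (8.5) get values and change from baseline for each parameter. Laboratory data (8.4) are classified for each parameter. The ECG (8.6) gets only an overall evaluation, as the echocardiogram does. None of the numeric echocardiographic parameters gets summary statistics. SAP section 10, which records changes from the protocol, does not mention the narrowing of tricuspid regurgitation to a peak velocity.

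**3. How much the overall reading can hide**

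A subject already rated abnormal CS at Screening has no worse level to move to. Let c be the share in that level at Screening and p the incidence of new valve injury, assumed unrelated to the Screening level. The rate that can show as worsening is at most p × (1 − c), so the visible fraction is at most 1 − c. The documents give neither c nor p, so both are assumptions here. The 406 used for n is the expected evaluable number at 6 months for the primary endpoint; the plan gives no number for the Month 12 echocardiogram.

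| c (assumed) | Visible fraction, at most | p = 1%: 406 × 0.01 = 4.06 injuries; visible, at most | Chance that at least one is visible, 1 − (1 − p(1 − c))^406 | p = 5%: 406 × 0.05 = 20.3 injuries; visible, at most |
|---|---|---|---|---|
| 0% | 1.00 | 4.06 | 0.98 | 20.3 |
| 50% | 0.50 | 2.03 | 0.87 | 10.15 |
| 80% | 0.20 | 0.81 | 0.56 | 4.06 |
| 95% | 0.05 | 0.20 | 0.18 | 1.02 |

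These are ceilings: they assume that every new injury in a subject with room to move does change the overall reading. They show that the answer turns on c. They do not estimate it.

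**4. Which visits are covered**

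The text of SAP 8.7 takes the shift to Month 12. The titles of tables 14.3.4.4.2 and 14.3.4.4.4 take it to every visit. The schedule in SAP Appendix 1 has echocardiograms through Year 5, while SAP 1.2 places the final analysis at Year 3. The Month 6 main analysis limits by-visit summaries to Visit 5, so it will contain no scheduled post-implant echocardiogram.

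**The case against.** A reader might infer that new valve damage would be invisible in the trial report. The documents do not support that. Valve injury is among the anticipated events that the protocol says will be collected, and reported cases are tabulated by preferred term, severity and relationship to the implant procedure. All serious events go to adjudication. A severe device-related case can count in a primary safety endpoint. Every echocardiographic value is listed.

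A reader might also infer that almost all NYHA III subjects start with an abnormal reading, so that the shift table cannot move. Protocol Appendix 14.2 links this class to structural heart disease, which makes abnormal readings plausible, but no distribution is given. The reading also has three levels, so a move from abnormal NCS to abnormal CS is visible. Nor does the Month 12 wording show that later echocardiograms are dropped, since the index says otherwise.

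It can further be said that SAP section 8 and Protocol 10.7 are general statements which the specific sections then apply, that the ECG section uses the same kind of summary, and that no control arm exists to separate implant effects from disease progression. The screening echocardiogram may also be up to six months old.

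These points narrow the concern and remove any claim about its size. One gap remains: a change that is measured but not reported as an adverse event is never aggregated, and the one aggregated measure cannot name a valve.

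**Conclusion.** The point holds in a limited form. Valve-specific echocardiographic change is collected and listed but not summarised or compared with Screening, although valve injury is a named risk of unknown frequency and echocardiography is a declared safety measure. New tricuspid or pulmonary regurgitation that no site reports as an adverse event would be found only by reading listings.

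The size is not determinable. It depends on the share already rated abnormal CS at Screening: if none are, that rating leaves every subject room to move; the nearer the share comes to all subjects, the less the shift table can show. No primary endpoint, hypothesis test or error rate is affected. The change is worth making because it is cheap and uses examinations already scheduled.

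**What to change.** In SAP 8.7 and the table index, for ITT and for Cohort #1:

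- Add descriptive statistics and change from Screening at Month 12 and Years 3, 4 and 5 for the numeric echocardiographic parameters, including tricuspid regurgitation peak velocity and the end-diastolic pulmonary regurgitation gradient.
- Restore tricuspid regurgitation, as in Protocol 8.1.10, to the parameter list beside peak velocity. If the CRF records a grade, add a shift table from Screening with the number worsening and a 95% confidence interval. If it records only peak velocity, state that leak severity cannot be assessed.
- Reconcile the text (shift to Visit 6) with the index (shift to every visit). Align the final analysis in SAP 1.2, now set at Year 3, with the echocardiograms scheduled for Years 4 and 5.
- Record the change of tricuspid parameter in SAP section 10.

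The cost is SAP wording and one or two descriptive tables, with no new procedure. What can be shown for tricuspid regurgitation depends on the CRF, which is not among the documents. The limits should be stated with the tables: local readings are noisy, the first scheduled post-implant echocardiogram is at Month 12, and without a control some worsening will be disease progression. The tables are descriptive only.

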8.8. Physical Examination

Complete physical examinations including body systems: general appearance, dermatological, lymphatic, head/ears/eyes/nose/throat (HEENT), chest/lungs, cardiovascular, abdomen, genitourinary/reproductive, musculoskeletal/extremities, neurologic/psychiatric and other) will be conducted at screening visits, Abbreviated physical examination will be conducted at all study visits as described in [Appendix 1: Time and Event Schedule](#), collecting only the changes from screening assessment.

In addition, chest circumference will be collected at screening.

Physical examination data will be summarized at screening visit, all data will be listed only.

This document is confidential.

9. Interim Analyses

Interim analysis is not planned.

This document is confidential.

10. Changes from Analysis Planned in Protocol

During the preparation of the SAP, it was realized that some additional analysis outside the protocol is needed. The respective analysis were introduced in the respective sections and are summarized below.

- 1) It was clarified that cardiac and all-cause mortality will be analyzed at 6 and 12 months post-implant visit, to be consistent with other efficacy analyses.
- 2) Two enrollment stopping rules will be considered during the study, both rules will be applied independently of each other and as well independent of the treatment group, see section 2.2. The enrollment stopping rules will ensure enrollment of sufficient number of subjects of certain population: at least 30 % women and at least 45 % HFpEF. This approach was previously confirmed by Sponsor with FDA.
- 3) Subgroup analysis was not clearly defined in the protocol: two population groups are of interest and were introduced in Section 5.6. This analysis is in line with the introduction of the enrollment stopping rules for the same populations, see Section 2.2.

This document is confidential.

11. Reference List

1. DSMB Statistical Analysis Plan Version 3.1 dated 07-Feb-2022
2. DSMB charter Version 4.0 dated 04-Mar-2022
3. Abraham, W. T., Adamson, P. B., Bourge, R. C., Aaron, M. F., Costanzo, M. R., Stevenson, L. W., CHAMPION Trial Study Group. (2011). Wireless pulmonary artery haemodynamic monitoring in chronic heart failure: a randomized controlled trial. *Lancet*, 377, 658-666.

12.1. General Considerations

- One SAS program will be created for each output.
- Each output will be stored in a separate file.
- Output files will be delivered in Word format (RTF). One portable document format pdf will be delivered for tables, listings, and figures.
- Numbering of TFLs will follow ICH E3 guidance

12.2. Table, Listing, and Figure Format

12.2.1. General

- All TFLs will be produced in landscape A4 format, unless otherwise specified.
- All TFLs will be produced using the Courier New font, size 9 which is the smallest acceptable point size for the Regulatory Authorities.
- The data displays for all TFLs will have a minimum blank 1-inch margin on all 4 sides.
- Headers and footers for figures will be in Courier New font, size 8 which is the smallest acceptable point size for the Regulatory Authorities.
- Legends will be used for all figures with more than 1 variable, group, or item displayed.
- TFLs will be in black and white (no color), unless otherwise specified
- Specialized text styles, such as bolding, italics, borders, shading, and superscripted and subscripted text, will not be used in the TFLs, unless otherwise specified. On some occasions, superscripts 1, 2, or 3 may be used.
- Only standard keyboard characters will be used in the TFLs. Special characters, such as non-printable control characters, printer-specific, or font-specific characters, will not be used. Hexadecimal-derived characters will be used, where possible, if they are appropriate to help display math symbols (e.g., μ).
- Mixed case will be used for all titles, footnotes, column headers, and programmer-supplied formats, as appropriate.

12.2.2. Headers

- All output should have the following header at the top left of each page:
- Endotronix Protocol ETX-HFS-PA-03 (Syneos Health study number 7000235)

This document is confidential.

- Draft/Final/Follow-up Run
- All output should have Pagen of Nat the top right corner of each page. TFLs are internally paginated in relation to the total length (i.e., the page number should appear sequentially as page n of N, where N is the total number of pages in the table).
- The date output was generated should appear along with the program name as a footer on each page.

12.2.3. Display Titles

- Each output is identified by the designation and a numeral (i.e., Table 14.1.1). ICH E3 numbering will be applied. The title is centered. The analysis set is identified on the line immediately following the title.

First Line of Title
Second Line of Title if Needed
(ITT Analysis Set)

12.2.4. Body of the Data Display

12.2.4.1. *General Conventions*

Data in columns of a table or listing are formatted as follows:

- Alphanumeric values are left-justified;
- Whole numbers (e.g., counts) are right-justified; and
- Numbers containing fractional portions are decimal aligned.

12.2.4.2. *Table Conventions*

- Units will be included where available
- Unless otherwise specified, only those categories for which there is at least 1 subject represented in 1 or more groups are included.
- Where percentages are presented in these tables, zero percentages will not be presented and so counts of 0 will be presented as 0 and not as 0 (0%).
- A Missing category is added to each parameter for which information is not available for 1 or more subjects.
- Unless otherwise specified, the estimated mean and median for a set of values are printed out to 1 more significant digit than the original values, and standard deviations are printed out to 2 more significant digits than the original values. The minimum and maximum should report the same significant digits as the original values.
- Percentage values are printed to one decimal place, in parentheses with no spaces, one space after the count (e.g., 7 (12.8%), 13 (5.4%)). Values that round down to 0.0 will be displayed as '<0.1'. Unless otherwise noted, for all percentages, the number of subjects in the analysis set for the given

This document is confidential.

group who have an observation will be the denominator. Percentages after zero counts should not be displayed and percentages equating to 100% are presented as 100%, without decimal places.

- Where a category with a subheading (such as system organ class) has to be split over more than one page, output the subheading followed by “(cont)” at the top of each subsequent page. The overall summary statistics for the subheading should only be output on the first relevant page.

12.2.4.3. *Listing Conventions*

- Listings will be sorted for presentation by subject number, visit/collection day, and visit/collection time.
- Dates are printed in SAS DATE9.format (“ddMMMyyyy”: 01JUL2000). Missing portions of dates are represented on subject listings as dashes (--JUL2000).
- All observed time values are to be presented using a 24-hour clock HH:MM or HH:MM:SS format (e.g., 11:26:45, or 11:26). Time will only be reported if it was measured as part of the study.
- Units will be included where available

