2.4.2 Additional Secondary Efficacy Endpoints

The first secondary efficacy endpoint is incidence of HF Hospitalizations or all-cause mortality at 12 months compared to a PG.

The mean 12 month event rate from the meta-analysis of prior control studies is 0.75, or 0.70 on an adjusted basis to account for SGLT-2i inclusion in the guidelines (Adjustment applied assuming 50% use of SGLT2i at the average hazard ratio observed across EMPEROR Preserved, EMPEROR REDUCED, DAPA-HF for NYHA III subjects.). A 12 month event rate of 0.70 represents a value just below the highest event rate observed across the CardioMEMS treatment studies (0.73 in MEMS-HF) and the upper bound of the overall meta-analytic treatment estimate (0.74). Taking the totality of results from the meta-analysis of active treatment trials, individual results of active treatment trials, as well as the meta-analysis of control trials, we set the secondary efficacy endpoint of performance goal (PG₁₂) at 0.70.

Furthermore, the mean 12- month event rate from the meta-analysis of prior treatment studies is 0.64, with both the CHAMPION (0.6) and GUIDE-HF (0.52, NYHA class III) treatment groups with event rates lower than the mean. The lowest 12 month event rate across CardioMEMS control studies of 0.63 occurred in GUIDE-HF (NYHA class III only), where modest use of SGLT2i occurred during the trial. We conservatively adjust this lowest observed control event rate down to 0.59 to account for increased SGLT2i utilization.

The table below outlines the data sources used to derive a PG for this endpoint.

Active Treatment - updated 12 Month Rates with calculation details

Study/Publication	Number of Subjects ¹	Events	Rate ²	Details
CHAMPION [7]	270	162	0.60	- HFH rate of 0.46, yielding approx. 124 events - Mortality rate of 0.14, yielding approx.38 events - Total events = 124 + 38
MEMS PAS [4]	1200	840	0.70	- HFH rate of 0.54, yielding 648 events - Mortality rate of 0.16, yielding 192 events - Total events = 648 + 192
MEMS-HF [5]	234	171	0.73	- HFH rate of 0.60, yielding 140 events - Mortality rate of 0.13, yielding approx. 30 events - Total events = 140 + 31
GUIDE-HF [8] – NYHA class III only	322	167	0.52	- HFH rate of 0.431 + plus death rate of 0.0897 - Composite rate = 0.52 - Total events = 322 subjects x 0.52
Estimate (CI)			0.64 (0.55, 0.74)	

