4.3. Modified Intent-to-Treat Population (mITT)

The Modified Intent-to-Treat Population (mITT) will include all implanted subjects from Cohort #2 and Cohort #3. All primary and secondary efficacy analyses as well as primary safety analyses will be performed on the mITT.

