5.3. Missing Data

It is anticipated that there will be little or no missing data that would impact the ability to assess the primary endpoint. The primary efficacy analysis will be based on the mITT population and the primary safety analyses will be based on the population of subjects who underwent a device implant. The primary analysis methods naturally handle missing data by censoring subjects who have dropped out. For the primary safety analyses, the endpoints can be considered as dichotomous and the extreme cases as well as a tipping point analysis can be presented.

For all other analysis, missing data will not be replaced.

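### The NYHA shift percentages describe assessed survivors only: subjects who died fall under Missing and leave the denominator, so a death row and a labelled second percentage are needed

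*SAP*

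**What the plan says.** The NYHA half of secondary efficacy endpoint 14 is a shift table by visit (SAP 7.1.17): "Shifts in NYHA functional classification from baseline over all post-baseline visits will be presented". The scale works by "placing subjects in one of four (I, II, III, IV) categories". Death has no category, and the section gives no rule for subjects who died before a visit.

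Three general rules fill that gap:

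- SAP 5.3, for everything outside the primary analyses: "For all other analysis, missing data will not be replaced".
- SAP 12.2.4.2, on percentages: "Unless otherwise noted, for all percentages, the number of subjects in the analysis set for the given", continuing over a page break, "group who have an observation will be the denominator". Section 7.1.17 does not override this default.
- SAP 12.2.4.2, on subjects without data: "A Missing category is added to each parameter for which information is not available for 1 or more subjects".

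The main analysis set is the mITT (SAP 4.3): "The Modified Intent-to-Treat Population (mITT) will include all implanted subjects from Cohort #2 and Cohort #3". Tables 14.2.2.14.1 to 14.2.2.14.5 repeat the shifts by sex, by ejection fraction, for the per-protocol set and for Cohort #1. Protocol 8.1.11 and SAP 7.1.17 both require class III at entry.

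**The concern.** A death before a visit is a known outcome. These rules treat it like a missed visit: it goes into the Missing count and out of the denominator. Because all subjects start in class III, the shift table is in effect one baseline row, and the share in class I or II is what a reader will take as the percentage improved for an endpoint named after improvement. That share covers only people who lived to be assessed.

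If the sickest subjects die, the remaining distribution looks better, and the effect grows as deaths accumulate at later visits. The choice of who is being described is left to a table-formatting default and is not stated in the endpoint section.

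**Working it through.** **Inputs.** No mortality assumption is given for this trial, so the figures come from the earlier device studies tabulated in SAP 2.4.1 and 2.4.2 (also Protocol 10.3 and 10.4).

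- Month 6 deaths: CHAMPION 15 of 270, MEMS PAS 107 of 1200, MEMS-HF 16 of 234. None is given separately for GUIDE-HF.
- Month 12 mortality: 0.14, 0.16, 0.13 and 0.0897 respectively.

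**The plan's own counts reproduce.** For CHAMPION the SAP states "Mortality rate of 0.14, yielding approx.38 events", and 270 × 0.14 = 37.8. For MEMS PAS, 1200 × 0.16 = 192, as stated. For MEMS-HF, 234 × 0.13 = 30.4; the plan shows 30 in one place and 31 in its total.

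**GUIDE-HF at Month 6.** The plan converts 12-month to 6-month rates by r6 = 1 − exp(ln(1 − r12)/2). Applying this to the death rate is my step: 1 − √(1 − 0.0897) = 0.0459.

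**Formula.** Let d be the proportion dead by the visit and p the proportion improved among assessed survivors, with no other missing data. If deaths count as not improved, the proportion improved is p(1 − d). The survivor-only figure is therefore higher by 1/(1 − d) − 1 in relative terms and by p × d in absolute terms. The last columns assume p = 50% for illustration.

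| Study | Month 6 d | Relative excess | 50% becomes | Month 12 d | Relative excess | 50% becomes |
|---|---|---|---|---|---|---|
| GUIDE-HF | 4.6% | 4.8% | 47.7% | 8.97% | 9.9% | 45.5% |
| CHAMPION | 5.6% | 5.9% | 47.2% | 14% | 16.3% | 43.0% |
| MEMS-HF | 6.8% | 7.3% | 46.6% | 13% | 14.9% | 43.5% |
| MEMS PAS | 8.9% | 9.8% | 45.5% | 16% | 19.0% | 42.0% |

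The relative excess is about 5 to 10% at Month 6 and 10 to 19% at Month 12. At p = 50% the absolute gap is 2.3 to 4.5 points at Month 6 and 4.5 to 8.0 points at Month 12.

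**Illustration.** Of 100 subjects due at Month 12, suppose 13 have died and 87 are assessed, 43 of them in class I or II. The default gives 43/87 = 49%; over assessed plus died it is 43/100 = 43%. The ratio is 1/(1 − 0.13) = 1.149.

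**The case against.** The case for leaving the tables alone has real weight.

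- **No improvement rate is planned.** The SAP defines no responder, threshold, test or power for NYHA. This stands: the excess applies to a percentage a reader would take from the table. With every subject starting in class III, though, that reading needs no derivation.
- **Deaths are reported elsewhere.** Table 14.1.1.3 gives numbers alive by visit for the mITT set, and Table 14.1.1.3.1 for Cohort #1. SAP 7.1.10 gives Kaplan-Meier mortality. Death also counts in the primary endpoint and the combined outcome. So a reader cannot say that deaths are hidden, and the Missing row shows that someone is absent. But that row does not separate deaths from missed visits, and the status table is not listed by sex, by ejection fraction or for the per-protocol set, where NYHA shifts are.
- **A summary while alive is legitimate.** NYHA class is undefined after death, and counting death as a failure is a different estimand. This stands too. The answer is to show both percentages, labelled, without replacing one by the other.
- **The layout cannot be checked.** Only table titles are available, and the denominator rule is a default. Even so, nothing in the text departs from it.

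Two stronger inferences fail. A reader might conclude that comparisons between Cohort #1 and Cohorts #2 and #3 are biased, but no NYHA comparison is planned: SAP 4.5 reports Cohort #1 separately, and SAP 4.6 assigns the Comparison Population to secondary endpoint 3. A reader might also take the Month 12 figure as the size of the problem in the main analysis, but SAP 1.2 limits its by-visit summaries to Month 6.

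**Conclusion.** The point holds as a gap in the presentation of a descriptive secondary endpoint. The NYHA percentages will describe assessed survivors, will not be labelled that way, and will not distinguish deaths from living subjects with no assessment.

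A reader might infer that this trial's improvement rate is inflated by 10 to 19%. The documents do not support that: the range is relative, belongs to Month 12, and rests on mortality borrowed from earlier studies. It also sets other missing data to zero and counts every death as not improved, which the SAP does not specify. For the main analysis the comparable figure is about 5 to 10% relative; the Month 12 range enters with the follow-up analysis. NYHA has no hypothesis test and lies outside the gatekeeping in SAP 2.4.2, so no success criterion depends on it. The change is worth making because it is cheap and removes an ambiguity that grows with follow-up.

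**What to change.** In SAP 7.1.17 and Tables 14.2.2.14.1 to 14.2.2.14.5:

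1. Add a Died row after class IV at each post-baseline visit, separate from a row for living subjects without an assessment.
2. Present percentages over subjects assessed plus subjects who died by that visit.
3. Beside these, keep the percentage among assessed survivors and label it as such.

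The death information is already collected and used for the primary endpoint (SAP 7.1), so no new data are needed. The cost is one extra row per table and a second percentage, and the percentage improved over assessed plus died will be somewhat lower than the survivor-only figure.
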